10.1 Assessment of Endpoints

10.2 Safety

Safety and tolerability of the study drug will be evaluated by analysis of adverse experiences, clinical laboratory tests, electrocardiogram, and physical examinations.

10.3 Efficacy

The sample size has been estimated assuming a standard deviation of 2.5 and a two sample t-test to have 80% power.

The protocol is designed to observe a 30% reduction in the number of voids compared to placebo following gene transfer using the following calculations with NCSS/PASS program (NCSS, Kaysville, Utah, 84037-3233).

Table 10;. Powering									
Power	N1	N2	Ratio	Alph	Beta	Mean	Mean2	S1	S2
0.80251	9	10	1.111	0.050	0.19749	10.0	6.6	2.5	2.5

The mean number of micturations per 24 hours will be evaluated at all visits and changes compared to baseline and placebo.

The other secondary outcome measures will be the change in the mean number of urge incontinence episodes per 24 hours; urgency episodes per 24 hours; mean volume voided per micturition, diminished urgency perception; change in weight of 72 hour pad test; and change in

detrusor overactivity (DO) including peak amplitude, volume at which DO appears and presence or absence of DO. The participants' perception of their bladder condition and response to treatment will be assessed at baseline (Week 0) and after 1, 2, 4, 8, 12, and 24 weeks. Improvement will be defined as a decrease of 1 point or more from baseline. Quality of Life (QoL) will be evaluated using the Kings Health Questionnaire (see Appendix B for algorithm). Change in maximum bladder capacity (difference of pre-treatment to post-treatment volume) as determined by cystometry of *hMaxi-K* versus pool of placebo participants from each treatment level.

Participants will be assessed for changes from baseline in urinary symptoms following administration of *hMaxi-K* using the questions of the ICIQ-SF form and the urgency rating scale. Participants will also be pooled across treatment groups (all active vs. all placebo).

10.4 Analysis of Endpoints

The methods described in this section will be updated during the course of the study. The final version of the statistical analysis plan (SAP) will be issued before the treatment code is broken.

This double blind, phase 1 study is designed to evaluate the safety of a single bladder injections of 2 different doses of *hMaxi-K* in individual participants. Both the safety data and data to assess efficacy will be analyzed using summary descriptive statistics for the two cohorts and the total study population. Associations between study therapy and the outcomes will be assessed using-repeated measures analyses, and explored in multivariate models, as needed.

11.1 Monitoring of Participant Safety

11.2 Informed Consent

The investigator will be responsible for obtaining from every participant prior to the participant's participation in the study a written Informed Consent signed and dated in accordance with U.S. federal regulations (21 CFR 50 and 21 CFR 312.60). The written Informed Consent will be obtained after the investigator has provided a full explanation, both verbally and in writing, of the purpose, risks and discomforts involved and potential benefits of the study to the participant. The original signed and dated copy of the Informed Consent must be maintained in the institution's records. The names of the participants enrolled during this study will be considered confidential.

11.3 Data Safety Monitoring Board (DSMB)

In order to monitor the safety of participants participating in this study, the sponsor will establish an independent Data Safety Monitoring Board (DSMB). The members will have training in medicine and/or gene therapy. All members will be independent of the study conduct.

The DSMB will review eligibility and all available safety data after the 5th participant has been administered study drug in the first dosing cohort. This first review will occur as soon as possible after the 5th participant's 3-Day Post-visit 2 telephone contact. Following their review of the

safety data, the DSMB will recommend whether enrollment into the first dosing cohort may proceed.

The DSMB will review participant's eligibility data and all safety data at 4 weeks following administration of study drug for the last participant enrolled into each dose cohort, in order to assess the need for modifications in safety monitoring and/or dosing. Following their review of the safety data for the last participant in the cohort at the 4th week post-dosing, the DSMB will recommend whether or not enrollment into the next dosing cohort may proceed (Section 5.2). The DSMB will also review the clinical safety data from the participants in all the dosing cohorts at the six month timepoint following the final dose.

12.1 Regulatory Standards

12.2 Electronic case report forms

An electronic case report form (E-CRF) will be completed for every participant who signed a written Informed Consent form and receives study drug. Any correction of data recorded onto the E-CRF will be entered in to the E-CRF which will create an electronic audit trail of the corrections and electronic signature of the study personnel who made the changes. For the long term follow-up period paper CRFs will be used.

The principal investigator must sign and date the certification form of each case report upon completion. This signature will indicate that thorough inspection of the data has been made and will thereby certify the contents of the electronic case report forms.

The investigator or institution will retain all original source documentation (e.g., laboratory results, treatment records, audit queries, etc.) unless specified otherwise by the protocol. The results as they become available will be entered on the appropriate electronic case report forms.

Electronic case report forms will be reviewed at the study site by a clinical monitor who will make a decision as to their acceptability in regard to completeness and accuracy of the data. Audit queries will be generated for omissions, corrections, and clarifications.

12.3 Clinical and Regulatory Monitoring

The study will be monitored in compliance with the relevant parts of 21 CFR and according to the ICH GCP Guidelines.

12.3.1 Study Conduct (Site)

Ion Channel Innovations will have an independent monitor, knowledgeable in GCP guidelines and regulations, monitor the clinical study. This representative of the sponsor (CE³ Inc.) will visit the institution prior to initiating the study and periodically thereafter to monitor acceptability of facilities, the agreement between E-CRF entries and original source documentation, adherence to the protocol, Good Clinical Practice (GCP) and to applicable FDA regulations and the maintenance of adequate clinical records. The monitor will have access to participant records, medication sheets, laboratory data, and other source documentation.

In addition to the initiation visit, the clinical sites will be audited after enrollment into each cohort has been completed. Once the study has been completed or terminated, a close-out or termination visit will be made. The Investigator and/or Study Coordinator will receive reasonable notification before each monitoring visit during the course of the study. At each visit, the Investigator will cooperate with the Sponsor's representative(s) for the review and verification of all E-CRFs, drug supply and inventory records, and any additional records requested for review. The monitor will ensure that all safety reports are submitted to the sponsor who is responsible for reporting required safety reports to the IRB, FDA, and OBA (see Section 12.2.2).

All information contained in a participant's E-CRF must have corresponding source documentation. This source documentation includes, but is not limited to, notes taken at participant visits recording the date of the visit, vital signs, physical findings, adverse events, or concomitant medications; laboratory reports; hospital records; and clinic records. Any correction of errors in the E-CRF will be first reviewed with the investigator prior to correction. The reason for any correction to the E-CRF will be noted along with the date and electronic signature of the person making the correction.

The records of the study may be participant to audit by Sponsor representatives (Clinical Quality Assurance or designee) or by government regulatory authorities (e.g. U.S. Food and Drug Administration). The Investigator agrees to allow access to the required participant records in the event of such an audit.

12.3.2 Adherence to Reporting Requirements

Ion Channel Innovations will have an independent monitor, knowledgeable in GCP guidelines and regulations, monitor adherence to the reporting requirements. This designee will ensure that the sponsor submitted any modifications to the protocol to the IRB and FDA. They will also review all safety reports submitted to the sponsor and ensure that those safety events requiring expedited reporting are submitted to the IRB, FDA, and OBA² within the required timeframes.

Within a reasonable time following completion of the study, a final study report will be written, reviewed by the sponsor's designee/CRO, and submitted to FDA.

12.4 Participant Confidentiality

Individual participant medical information obtained as a result of this study is considered confidential and disclosure to third parties, other than those cited below, is prohibited. Participant confidentiality will be further ensured by utilizing participant identification code numbers for all reports.

In compliance with regulatory guidelines regarding the monitoring of clinical studies and in fulfillment of the Investigator's obligations to Ion Channel Innovations, it is required that data generated as a result of the study be available for inspection, on request, by personnel from Ion Channel Innovations and regulatory agencies. These shall include all study-relevant documentation, including medical histories to verify eligibility, laboratory test results to verify

² OBA is the Office of Biotechnical Activities of the National Institutes of Health (NIH) which includes NIH Genetic Modification Clinical Research Information System (GeMCRIS); OHSR is the Office of Human Subject Research, NIH.

transcription accuracy, treatment and diagnostic reports, admission/discharge summaries for hospital admissions occurring while the participant is on-study, and autopsy reports (if available) for deaths occurring during or in temporal proximity to the study.

As part of the required content of the informed consent, participants must be informed that their records will be reviewed by Ion Channel Innovations and regulatory agencies. Should access to medical record require a separate waiver or authorization, it is the Investigator's responsibility to obtain such permission from the participant in writing before the participant is entered into the study.

12.5 Records

The Food and Drug Administration requires that an investigator retain records for a period of two (2) years following the date a New Drug Application or Product License Application is approved for the drug for the indication for which it is being investigated; or, if no application or license is to be filed or, if the application or license is not approved for such indication, until two (2) years after the investigation is discontinued (21 CFR 312.62).

The investigator should ensure that the following records are maintained:

Participant files containing copies of completed case reports and supporting documentation and a copy of the signed, Informed Consent form.

Investigator files containing copies of the documents required for the initiation of the study (executed form FDA 1572, signed Investigator's Agreement, Curricula Vitae for the principal investigator, copy of the IRB approval of the protocol and Informed Consent forms), copies of correspondence received from and sent to Ion Channel.

Pharmacy files containing copies of the record of use for the Investigational Drug, instructions for completion of these records, and the Investigator's Brochure.

APPENDIX A Grading of Adverse Events

PARAMETER	GRADE 1 MILD	GRADE 2 MODERATE	GRADE 3 SEVERE	GRADE 4 POTENTIALLY LIFE-THREATENING
HEMATOLOGY				
Hemoglobin	10.0 g/dL – 11.0 g/dL OR any decrease \geq 2.5g/dL	9.0 g/dL – 9.9g/dL OR any decrease \geq 3.5g/dL	7.0 g/dL – 8.9g/dL OR any decrease \geq 4.5g/dL	< 7.0 g/dL
WBC—Elevated	13,000 – 14,999/mm ³	15,000 – 19,999/mm ³	20,000 – 24,999/mm ³	> 25,000/mm ³
WBC—Decreased	2001 – 2499/mm ³	1501 – 2000/mm ³	1000 – 1500/mm ³	< 1000/mm ³
Platelets—Decreased	100,000 – 124,999/mm ³	50,000 – 99,999/mm ³	25,000 – 49,999/mm ³	< 25,000/mm ³
Platelets—Elevated	NA	550,000 – 600,000/mm ³	> 600,000/mm ³	NA
PT	1.1-1.24 X ULN	1.25 – 1.49 X ULN	1.5 – 3.0 X ULN	>3.0 XULN
PTT	>1 – 1.5 X ULN	>1.5 – 2.0 X ULN	>2 X ULN	-
CHEMISTRIES				
BUN	25 - 30 mg/dL	31 - 40 mg/dL	41 – 50 mg/dL	>50 mg/dL
LDH	1.5 – 2.5 X ULN	2.6 – 3.5 X ULN	3.6 – 5.0 X ULN	>5.0 X ULN
Hyponatremia	<LLN – 130 mEq/L	123 – <130 mEq/L	116 – <123 mEq/L	<116 mEq/L
Hypernatremia	>ULN – 150 mEq/L	>150 – 155 mEq/L	>155 – 160 mEq/L	>160 mEq/L
Hyperkalemia	>ULN – 5.5 mEq/L	>5.5 – 6.0 mEq/L	>6.0 – 7.0 mEq/L	>7.0 mEq/L
Hypokalemia	<LLN – 3.2 mEq/L	3.0 – <3.2 mEq/L	2.5 – <3.0 mEq/L	<2.5 mEq/L
Bicarbonate (serum)	<LLN – 16 mEq/L	10 – <16 mEq/L	8 – < 10 mEq/L	<8 mEq/L
Phosphate	<LLN – 2.5 mg/dL	\geq 2.0 – <2.5 mg/dL	\geq 1.0 – <2.0 mg/dL	<1.0 mg/dL
Hypocalcemia	<LLN – 8.0 mg/dL	7.0 – <8.0 mg/dL	6.0 – <7.0 mg/dL	<6.0 mg/dL
Hypercalcemia	>ULN – 11.5 mg/dL	>11.5 – 12.5 mg/dL	>12.5 – 13.5 mg/dL	>13.5 mg/dL
Magnesium	<LLN - 1.2 mEq/L	0.9 – <1.2 mEq/L	0.7 – <0.9 mEq/L	<0.7 mEq/L
Total bilirubin	>ULN – 1.5 X ULN	>1.5 – 3.0 X ULN	>3.0 – 10.0 X ULN	>10.0 X ULN
Hypoglycemia	<LLN - 55 mg/dL	40 - <55 mg/dL	30 – <40 mg/dL	<30 mg/dL
Hyperglycemia (nonfasting & no history of diabetes)	>ULN – 160 mg/dL	>160 – 250 mg/dL	>250 – 500 mg/dL	>500 mg/dL
CPK	>ULN – 2.5 X ULN	>2.5 – 5.0 X ULN	>5.0 - 10.0 X ULN	>10 X ULN
Creatinine	>1.0 – 1.5 X ULN	>1.5 – 3.0 X ULN	>3.0 – 6.0 X ULN	>6.0 X ULN
AST (SGOT)	ULN – 2.5 X ULN	>2.5– 5.0 X ULN	>5.0 – 20.0 X ULN	> 20.0 X ULN
ALT (SGPT)	>ULN – 2.5 X ULN	>2.5 – 5.0 X ULN	>5.0 – 20.0 X ULN	> 20.0 X ULN
GGT	>ULN– 2.5 X ULN	>2.5 – 5.0 X ULN	>5.0 – 20.0 X ULN	>20.0 X ULN
Alkaline Phosphatase	>ULN – 2.5 X ULN	>2.5 – 5.0 X ULN	>5.0 – 20.0 X ULN	>20.0 X ULN

PARAMETER	GRADE 1 MILD	GRADE 2 MODERATE	GRADE 3 SEVERE	GRADE 4 POTENTIALLY LIFE-THREATENING
URINALYSIS				
Proteinuria (random urine sample)	1+	2-3+	4+	-
Microscopic RBC (exception is urine sample post-catherization)	6 – 10 RBC/hpf	>10 RBC/hpf	Gross hematuria	-
CARDIOVASCULAR				
Hypertension	Asymptomatic, transient (<24 H) increase by >20 mmHg (diastolic) or >150/100 if previously WNL; not requiring treatment	Recurrent or persistent (>24H) or symptomatic increase by >20 mmHg (diastolic) or to >150/100 if previously WNL; may require monotherapy	Requiring more than one drug or more intensive therapy than previously	Life-threatening consequences (e.g., hypertensive crisis)
Hypotension	Transient orthostatic hypotension, intervention not indicated	Symptoms corrected with oral fluid replacement	IV fluid required; hospitalization not required	Hospitalization required
Conduction abnormality/atrioventricular heart block	Asymptomatic, no intervention indicated	Non-urgent medical intervention indicated	Symptomatic & incompletely controlled medically or controlled with device (e.g., pacemaker)	Life-threatening
Prolonged QTc interval	Asymptomatic, QTc interval 0.45 – 0.48 sec	Asymptomatic, QTc interval >0.48 sec	Symptomatic	Life-threatening (e.g., arrhythmia associated with CHF, hypotension, syncope, shock)
Supraventricular & nodal arrhythmia	Asymptomatic, no intervention indicated	Symptomatic, but not requiring treatment	Symptomatic & incompletely controlled medically or controlled with device (e.g., pacemaker)	Life-threatening (e.g., arrhythmia associated with CHF, hypotension, syncope, shock)
Ventricular arrhythmia	Asymptomatic, intervention not indicated	Symptomatic, but not requiring treatment	Symptomatic & incompletely controlled medically or controlled with device (e.g., pacemaker)	Life-threatening (e.g., arrhythmia associated with CHF, hypotension, syncope shock)
Cardiac Arrhythmia – Other	Asymptomatic, not requiring treatment	Symptomatic, but not requiring treatment	Symptomatic, and requiring treatment of underlying cause	Life-threatening (e.g., arrhythmia associated with CHF, hypotension, syncope, shock)
Cardiac ischemia/infarction	Asymptomatic arterial narrowing without ischemia	Asymptomatic and testing suggests ischemia	Asymptomatic ischemia (angina) or testing consistent with ischemia, intervention indicated	Acute myocardial infarction

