- b. Cystometry includes: volume at first desire to void, detrusor pressure, abdominal pressure, detrusor pressure at beginning of voiding, detrusor pressure at maximum flow, maximum detrusor pressure, volume at strong urge to void, peak flow rate during voiding, voided volume, volume at DO, post-void residual volume, total bladder volume (voided volume + residual volume), number of detrusor contractions during procedure and duration of DO
- c. Inclusion criteria specify residual volume ≤200 ml. Bladder scans at V1 and V8 to be done before catheterization.
- d. Urinalysis with microscopic RBC and WBC, protein, glucose, nitrites, pH, and specific gravity at V 1, 3-5 and V7 and V8. At V1A and V2, urinalysis by Dipstick will be done. Urine cultures at V1 (by catheterization with the urodynamic catheter), V3 (clean void); at V1A, V2, V5 and V8 prior to cystometry or cystoscopy (by catheterization with the urodynamic catheter) and before discharge by clean void (at V2 use first voided urine after drug administration). Visit 2 urinalysis by Dipstick will be done prior to dosing and urine culture will be performed both prior to study drug administration and prior to discharge
- e. Lab tests to be done at V1, V2 - 5, V7 and V8 include: Hematology- CBC with differential, platelet count, sedimentation rate, PTT, PT (no PT and PTT at V2 and V4), CRP, Antinuclear antibody; Fasting chemistry- BUN, creatinine, Na⁺, K⁺, Mg⁺⁺, Ca⁺⁺, CO2, Cl⁻, albumin, alkaline phosphatase, ALT, AST, GGT, total bilirubin, total protein, CPK, LDH, glucose; Serum Pregnancy Test for beta-HCG required for women of child bearing age who have not had hysterectomy at Screening V1 and on as need basis. In addition, FSH> 40 IU/L if last menstrual cycle not > 12 months prior to study enrollment. HbA1c will be done at screening Visit 1 only. No chemistries will be done at 2 (Week 0). At V4, chemistries will include only BUN, creatinine, electrolytes (Na⁺, K⁺), CRP, glucose, and ANA. No lab tests will be done at Visit 1A or V6. Lab tests should be taken at the same time of day at all study visits.
- f. Test or procedure will be done prior to administration of study drug at Visit 2. At V2 there is also a urine culture after dosing.
- g. At V2, blood and urine pre-dosing and at 2 hour post-dosing. If specimen is still positive at week 24, participant must return monthly until two successive specimens are negative for *hSlo* DNA.

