The lot # for *hMaxi-K* used in this study is FIN0400 and the lot # for PBS-20% sucrose is FP-012-092906.

The gene product or PBS-20% sucrose will be prepared and administered in the same manner as Botox® is administered in the office. The participant kit will be taken from the freezer and the vials warmed to room temperature and the cap of the vial will be wiped with alcohol. The 2 or 3 vials in the kit will be administered sequentially. This sequential administration of vials for a total of 4 ml or 6 ml volume maintains the study blind while minimizing the risk for bacterial contamination that could occur if the vials were mixed prior to administration.

To minimize the possibility of dehydration and/or a vasovagal response after required blood collections or the *hMaxi-K* administration, participants will be instructed to eat breakfast and abstain from any alcohol products on that morning.

The investigator (or designee) should administer the drug and must remain blinded. The investigator's pharmacy or a designee will be responsible for dispensing the drug in a timely fashion for use on the day of the participant's Visit 2 and accounting of all drug provided by the sponsor. Records of document control numbers and dates received will be kept on a Drug Inventory Form provided by the sponsor for accounting purposes. Under no circumstances will the investigator supply study drug to other investigators, allow study drug to be used other than directed by this protocol, or destroy or dispose of study drug in any other manner without prior written authorization from the sponsor.

All partially used clinical trial kits will be accounted for and destroyed at the investigative site according to IBC guidance. The investigator or designee, upon completion of the drug accounting process, will send all unused clinical materials back to the Sponsor or designee for disposition.

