5.2.1 Stopping Rules

No acute toxicity was seen in the preclinical studies in rats with administered intravenous doses up to 1000 µg (approximately 1500 µg/kg in the rat). Potential toxicities would be those that could occur (1) because of enhanced efflux of K^+ with resultant decreased intracellular Ca^{++} concentration, thus altering smooth muscle function in diverse organ systems; (2) reaction to the naked DNA.

In the event that any participant experiences one of the following events, **no** additional participants will be accrued and **no** further doses of hMaxi-K will be administered until the DSMB and FDA have reviewed the case and have provided their recommendation to the sponsor.

- 1) Urinary retention, i.e., the inability to micturate for more than 12 hours with a urine bladder volume (greater than 400 ml established by bladder scan) that requires placement of a bladder drainage catheter.
- 2) Any adverse event of Grade 2 that last longer than 96 hours or Grade 3 or higher in the blood chemistry, completed blood count or urine categories of adverse event criteria listed in Appendix A.
- 3) In the event of a clinically significant sign or symptom reported by the site PI to the medical monitor in any of the first four participants of each cohort unless permission is given by the medical monitor.
- 4) Bladder pain and /or irritation that persists for four hours or more after gene transfer that is thought by the Principal Investigator not to be related to acute trauma from the cystoscopy, direct bladder muscle injections, and catheterization.

Clinical data regarding the event will be collected, reviewed, and discussed with DSMB and FDA. After review of these data with FDA the clinical study may resume **only** with concurrence of FDA.

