6.6 Laboratory Safety Tests

Laboratory safety tests will be performed at Screening (V1), Baseline (V2) and 1 (V3), 2 (V4), 4 (V5), 12 (V7), and 24 (V8) weeks post dosing with study drug.

The laboratory safety tests include:

- Hematology: V1, V2-V5, V7-V8; Complete blood count (CBC) with differential, platelet count, sedimentation rate (sed. rate), PT and PTT (no PT and PTT at V2 and V4).
- Fasting chemistry: V1, V3-V5, V7-V8; Blood Urea Nitrogen (BUN), creatinine, electrolytes (Na⁺, K⁺, Mg⁺⁺, Ca⁺⁺, CO₂, Cl), albumin, alkaline phosphatase, ALT, AST, GGT, LDH, CPK, total bilirubin, total protein, C-reactive protein (CRP), antinuclear antibody (ANA), and glucose. V4 chemistry testing: Blood Urea Nitrogen (BUN), creatinine, electrolytes (Na⁺, K⁺), C-reactive protein (CRP), glucose, and ANA only.
- At screening, participants of child bearing years must have a serum pregnancy test for beta- HCG if they have not had a hysterectomy. In addition, they must have either a serum FSH >40 IU/L or a history of no menses for more than 12 months to confirm post-menopausal status if a hysterectomy or bilateral tubal ligation has not been done.
- At screening only, participants must have a serum hemoglobin A1c performed

- Urine analysis; Conducted at V1, V1A (by dipstick), V2 (by dipstick), V3-V5, V7-V8; microscopic RBC and WBC, protein, glucose, nitrites, pH, and specific gravity. Dipstick will measure blood, leukocyte esterase and nitrites.
- Urine culture: At Screening Visit 1 and 1A (collect by catheterization) and at V3. At Visit 1A, Visit 5 and Visit 8, prior to cystometry (collect using urodynamic catheter) and repeated with clean void prior to discharge. At Visit 2, collect using urodynamic catheter prior to cystoscopy and first clean voided urine after study drug dosing. If V1A cystometry performed at V1 then urine cultures pre-and post-cystometry should be done using urodynamic catheter before cystometry and repeated with clean void prior to discharge.

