6.9 Laboratory Evaluations

A local safety laboratory (for example Quest) will perform analysis of all blood and urine specimens. The blood samples for the safety laboratories evaluations should be taken when the participant is fasting if possible. In addition, the participant should be asked to not perform any strenuous exercise or activities prior to blood sampling.

The urine analysis done immediately prior to cystometry and drug administration will be performed by the PI with a Dipstick™ to see if the Dipstick™ is positive for leucocytes and

nitrites which may be a sign of infection. A spun microscopic evaluation may be required for further evaluation,

Urine and blood specimens that are collected from the participants will have real time PCR testing done for detection of *hSlo* cDNA in the Urology laboratory at the Albert Einstein College of Medicine. It is anticipated that the following amounts of blood will be collected for the following procedures over the 6 month study participation:

Table 8. Blood collection (minimum amount of blood that should be taken)			
Procedure	Visit number	Blood volume drawn (mL)	Total blood volume drawn (mL)
Chemistry	1, 3, 4, 5, 7 and 8	15	90
Hematology	1, 2, 3, 4, 5, 7 and 8	3.0	21
Blood for analysis of hSlo cDNA)	2 (pre- and 2 hr post-dosing), 3, 4, 5, 6, 7 and 8	0.5	4
Minimum volume of blood drawn for study over 6 months:			115 ml

Table 9. Summary of Laboratory Tests By Visit								
	Chemistry Fasting	Hematology	βHCG	HA1c	FSH	Urine Cultures	hSlo Blood/ urine	Urinalysis
Visit 1	◆	◆	◆	◆	◆	1 (one from catheter drainage) – after bladder scan		◆
Visit 1A Cystometry						2 (one from catheter drainage pre-cystoscopy and 1 from first clean void post-cystoscopy)		via dipstick
Visit 2 (Treatment by Cystoscopy)		◆ No PT/PTT				2 (one from catheter drainage pre-treatment and 1 from first void post-treatment)	◆ (blood and urine: pre-dosing and 2 hours post-dosing)	via dipstick (prior to treatment)
Visit 3	◆	◆				1 (clean void)	◆	◆
Visit 4	◆	◆ No PT/PTT					◆	◆
Visit 5 Cystometry	◆	◆				2 (one from catheter drainage pre and 1 from first clean void post)	◆	◆
Visit 6							◆	
Visit 7	◆	◆					◆	◆
Visit 8 Cystometry	◆	◆				2 (one from catheter drainage pre and 1 from first clean void post-treatment); Bladder scan prior to catheterization	◆	◆

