7.6 Visit 3 (Study Week 1 +2 days)

The following tests and evaluations will be performed:

- Review medical history for events since last visit;
- Review concomitant meds since last visit;
- Review voiding diaries;
- Participants complete global assessment of disease state and response to treatment;
- Physical examination including urogenital examination and vital signs
- Electrocardiogram;
- Obtain blood for the following laboratory determinations:
 - Hematology: Complete Blood Count (CBC) with differential, platelet count, sedimentation rate (sed rate), PT and PTT.
 - Fasting chemistry: Blood Urea Nitrogen (BUN), creatinine, electrolytes (Na⁺, K⁺, Ca⁺⁺, Mg⁺⁺, CO₂, Cl), albumin, alkaline phosphatase, ALT, AST, GGT, LDH, CPK, total bilirubin, total protein, C-reactive protein (CRP), antinuclear antibody (ANA), and glucose;
- Obtain urine for routine urine analysis: microscopic RBC and WBC, protein, glucose, nitrites, and specific gravity, pH;
- Collect and weigh pads used for 72 hours;
- Obtain urine and blood specimen for analysis of *hSlo* cDNA with PCR;
- Obtain urine culture by clean void;

- Provide patient with diary materials;
- Instruct the participant to complete daily voiding diaries for 7 days prior to next visit and return with results at next visit including pads used for 72 hours prior to that visit (and clean pad to be used as a baseline). The site must call participants at least 7-8 days prior to next scheduled visit to remind patient to complete the diaries for 7 days prior to next visit;

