9.5 Severity of Adverse Event

Adverse events included in the toxicity table (Appendix A) will be graded according to the definitions provided. For adverse events not listed in the toxicity table, assignment of grade based on intensity of symptoms, degree of limitation of usual daily activities, or level of abnormality of objective clinical signs or laboratory parameters will be according to severity using the following criteria:

- Grade 1: transient or minimal symptoms; not interfering in function or ability to perform activity of daily living or require a medication change. No medical intervention required.
- Grade 2: symptoms interfering in function but not with activities of daily living. Minimal or no medical intervention required.
- Grade 3: incapacitating symptoms that interfere with function and activities of daily living; required bed rest and/or resulted in loss of work or cancellation of social activities. Medical intervention required. Hospitalization possible.
- Grade 4: Medical intervention is required to prevent permanent impairment or death; OR Permanently Disabling: bed-ridden or disabling, significant medical intervention/therapy required, hospitalization or hospice care possible.

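### Appendix A's only hyperglycaemia row leaves out fasting samples and women with diabetes, so on a literal reading the Grade 3 limb of stopping rule 2 does not reach the glucose tests as scheduled

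*Protocol*

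**What the plan says.** **Grading.** The chemistry part of Appendix A has one row for high glucose, "Hyperglycemia (nonfasting & no history of diabetes". Its bands are Grade 1 above the upper limit of normal to 160 mg/dL, Grade 2 above 160 to 250, Grade 3 above 250 to 500, and Grade 4 above 500. SAP 10.2 also sends the grading of clinically significant laboratory abnormalities to Appendix A.

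**Halt.** Under rule 2 of Protocol 5.2.1, one trigger is "Grade 3 or higher in the blood chemistry, completed blood count or urine categories of adverse event criteria listed in Appendix A". Accrual and dosing then stop until the DSMB and FDA have reviewed the case, and resumption needs FDA agreement. A second trigger in the same rule is a Grade 2 event that persists beyond 96 hours.

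**Sampling.** Section 6.6 schedules "Fasting chemistry: V1, V3-V5, V7-V8" and includes glucose in that panel. The visit lists repeat the label, for example "Fasting chemistry: Blood Urea Nitrogen (BUN), creatinine, electrolytes" at Visit 3. Section 6.9 softens it: "The blood samples for the safety laboratories evaluations should be taken when the participant is fasting if possible". At the dosing visit, Table 1 footnote e says "No chemistries will be done at 2 (Week 0".

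**Who can enrol.** Exclusion 12 in section 4.3 bars people with diabetes only when HbA1c is above 7%.

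**Fallback.** Section 9.5 grades events that are not in the toxicity table, and one of the bases it allows is "level of abnormality of objective clinical signs or laboratory parameters".

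**The concern.** The row that sets the glucose threshold for an automatic halt describes a kind of sample that the plan does not schedule after dosing, and a group that does not include every eligible woman. No reason is given for grading a non-fasting 300 mg/dL and leaving a fasting 300 mg/dL ungraded; the fasting value is at least as abnormal.

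What is at stake is narrow. Rule 2 takes the decision to continue away from the sites, the medical monitor and the sponsor, and gives it to the DSMB and FDA. If a high glucose falls outside the rule because of a row label, the value can still be acted on, but the automatic stop and the FDA review may be lost. With up to six sites, the label could also be applied differently from one site to another.

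**Working it through.** No figure in the plan needs to be reproduced. The check is a comparison of texts with a few counts.

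**1. Is the row unusual in its own table?** Appendix A has 20 chemistry rows: BUN, LDH, low and high sodium, high and low potassium, bicarbonate, phosphate, low and high calcium, magnesium, bilirubin, low and high glucose, CPK, creatinine, AST, ALT, GGT and alkaline phosphatase. One of the 20, high glucose, is limited by fasting state or medical history. The low-glucose row just above it has no such limit.

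**2. Does the row fit the scheduled samples?**

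| Post-dose visit | Glucose scheduled | Panel heading |
|---|---|---|
| V3 (week 1) | yes | fasting |
| V4 (week 2, reduced panel) | yes | fasting |
| V5 (week 4) | yes | fasting |
| V6 (week 8) | no chemistry | – |
| V7 (week 12) | yes | fasting |
| V8 (week 24) | yes | fasting |

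Five of five are labelled fasting. The instruction that "participants will be instructed to eat breakfast and abstain from any alcohol products on that morning" stands in the drug administration text, and the dosing visit has no chemistry, so it does not clearly create a scheduled non-fasting glucose.

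**3. What happens to one value, 300 mg/dL, read literally?**

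| Sample | Appendix A grade | Grade 3 limb of rule 2 |
|---|---|---|
| Non-fasting, no diabetes | 3 (>250–500) | met |
| Fasting, no diabetes | none | not met by itself |
| Fasting or non-fasting, history of diabetes | none | not met by itself |

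**4. Does section 9.5 close the gap?** It lets an investigator grade an unlisted laboratory value by how abnormal it is. But its four grade descriptions speak of symptoms, function and intervention and give no glucose figure, and rule 2 names Appendix A rather than 9.5. Whether a 9.5 grade counts for rule 2 is not stated.

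**5. How many tests are involved?** With full enrolment and no replacements, 18 participants × 5 visits = 90 scheduled post-dose glucose tests. In cohort 1, 9 × 3 (V3, V4, V5) = 27 of them fall due by the week 4 DSMB review that must precede escalation (section 5.2.2). These are counts of tests, not of high values. The documents give no rate of glucose above 250 mg/dL.

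**The case against.** The strongest reply is that rule 2 can be read as naming categories of event. A high glucose is a blood chemistry event; section 9.5 supplies a grade where the table has none; so a Grade 3 fasting value would halt the trial. The Grade 2 limb can likewise be read as independent of Appendix A, so a persistent high value graded 2 would also stop dosing. Both readings are tenable, which is why the point is one of unclear text and not of a rule shown to fail. They still leave the grade to judgement where the table offers a number.

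Further points that stand:
- Fasting is asked for only if possible, so a sample that was in fact non-fasting, from a woman without diabetes, would be graded as written. Samples taken as planned are the ones without a grade.
- Other controls apply. Rule 3 covers a clinically significant sign or symptom in the first four participants of each cohort, although the medical monitor may permit continuation and 9 − 4 = 5 participants per cohort lie outside it. The medical monitor can hold enrolment at any time for a clinically serious sign or symptom. The DSMB reviews safety data after the fifth participant and again at week 4 after the cohort's last dose.
- Other scheduled tests, such as CRP, ANA and albumin, also have no Appendix A row. Glucose differs because the table sets numeric halt levels for it and then limits them to samples that the plan does not schedule.
- The event is remote. Exclusions 11 and 12 remove clinically significant screening abnormalities and poorly controlled diabetes. The protocol reports no clinically significant shift to abnormal chemistry in the first stage of the study in men (doses up to 7500 µg), and the adverse events listed for the earlier OAB trial include no hyperglycaemia.

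A reader might infer that a dangerous glucose would go unnoticed, or that escalation to 24000 µg would proceed without these results. The documents do not support either. The 27 cohort 1 tests fall due before the DSMB decides on escalation, and that review covers all unblinded safety data.

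**Conclusion.** The mismatch is plain in the text: one high-glucose row, limited to non-fasting samples in women without diabetes, against five of five post-dose tests labelled fasting and an eligibility rule that admits some women with diabetes. Read literally, a fasting glucose above 250 mg/dL, or any high glucose in a woman with diabetes, does not by itself meet the Grade 3 limb of rule 2. It gets there only if a section 9.5 grade is accepted for that rule, and the protocol does not say whether it is.

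This is a low-priority safety correction. What may be lost is the automatic halt with FDA review, not detection of the value. The conclusion assumes that samples are taken fasting as headed and that the row label is applied as written. It assumes nothing about how often such values occur, except that they are likely to be rare. The Grade 2 limb is affected only if the Appendix A restriction is read to govern it as well.

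**What to change.** Amend the Appendix A row in two ways:

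1. Remove the non-fasting limit, so that at least the existing Grade 3 (>250–500 mg/dL) and Grade 4 (>500 mg/dL) cut-points apply to any scheduled glucose.
2. State that the same Grade 3 and Grade 4 cut-points apply to women with a history of diabetes.

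Lower fasting bands for Grades 1 and 2 are optional. Without them a fasting value up to 160 mg/dL stays Grade 1, which is lenient but does not affect the Grade 3 halt.

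Keep the change to glucose. A general sentence making every section 9.5 chemistry grade count for rule 2 would go too far: section 6.6 puts CRP and ANA in the chemistry panel, neither has an Appendix A row, and an investigator-judged grade for either could then stop the trial until FDA agrees to resume.

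The cost is a short protocol amendment, with no new tests or visits. SAP 10.2 refers to Appendix A and would follow without change. The downside is a rare extra pause for DSMB and FDA review, which is what rule 2 is meant to produce.
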